#### **6.6.5. Digital Reading Index and Visual Function Application**

The digital reading index will only be analyzed at the Month 24 reporting while the digital visual functional application will be analyzed at both the Month 12 and Month 24 reporting.

Descriptive summary statistics for baseline, absolute values and change from baseline data to Month 12 and Month 24 will be provided by treatment group for digital reading index.

Additionally, the average digital reading index score over the last 3 months for each reporting period (Month 10 - Month 12 for the Month 12 reporting; Month 22 - Month 24 for the Month 24 reporting) will be calculated for each subject who has at least one digital reading index assessment in these windows. The observed values for the digital reading index and changes from baseline will be summarized by treatment group. Summaries will present the descriptive statistics for baseline, absolute values and change from baseline data.

Descriptive summary statistics for baseline, absolute values and change from baseline data to Month 12 and Month 24 will be provided by treatment group for digital visual function.

Additionally, the average digital visual function score over the last 3 months for each reporting period (Month 10 - Month 12 for the Month 12 reporting; Month 22 - Month 24 for the Month 24 reporting) will be calculated for each subject who has at least one digital visual function assessment in these windows. The observed values for the digital visual function and changes from baseline will be summarized by treatment group. Summaries will present the descriptive statistics for baseline, absolute values and change from baseline data.

#### **6.6.6. Genetic Polymorphisms**

The genetic polymorphisms data will be analyzed and reported in a separate report and briefly summarized in the clinical study report (CSR). The genetic polymorphisms data will be listed for the genotyping set.

### **6.6.7. Dry AMD Analysis**

Biomarkers of early and intermediate stage of AMD outside the GA area will also be evaluated in this study. The number and percentage of subjects with at least one lesion (up to 5) area in the study eye classified as iRORA will be summarized at baseline by treatment group in the mITT set. The number and percentage of subjects with a progression from iRORA to cRORA based on SD-OCT in the study eye will be summarized over time by treatment group. A CMH test with the number of baseline iRORA lesions (0, 1, 2, 3, 4,  $\geq 5$ ), presence of CNV in the fellow eye (yes or no), and baseline GA lesion area ( $< 7.5 \text{ mm}^2$  or  $\geq 7.5 \text{ mm}^2$ ) as the stratification factors will be presented for each post-baseline visit. If necessary due to sparse cells, an unadjusted analysis may be performed. In addition, the percentage of baseline lesions with a progression will also be presented over time by treatment group.

The above summary and analysis will also be repeated in those subjects with at least one lesion in the study eye classified as large drusen at baseline and whether these progressed to iRORA or cRORA in the study eye. Large drusen is defined as a drusen that is greater than or equal to 40 microns in height on SD-OCT.

This analysis will not be conducted at the Month 12 reporting and will only be conducted for the final study reporting.

All dry AMD data will be listed for the ITT set.

### **6.6.8. Analyses of Other Ophthalmology Efficacy Imaging Data**

In addition to the GA lesion(s) size data from the FAF, analysis of additional efficacy parameters will be performed from this imaging instrument for the mITT set. The following summaries will be performed separately by study eye and by fellow eye and will be presented by treatment group.

- Descriptive summary statistics for baseline, absolute values and change from baseline data for the distance of GA lesion from atrophy junction to the fovea in study eyes with non-subfoveal involvement of the GA lesion at baseline (assessed from FAF). For the fellow eye, this will be presented for fellow-eyes with non-subfoveal involvement of the GA lesion at baseline. Non-subfoveal involvement is defined as distance of the atrophy junction to the fovea  $> 0$ .
- Conversion from non-subfoveal involvement to subfoveal involvement of the GA lesion at each visit (assessed from FAF). This will include only study eyes with non-subfoveal involvement for GA lesions at baseline. For the fellow eye, this should be presented for fellow eyes with non-subfoveal involvement at baseline. This will be presented as a cumulative incidence at each scheduled visit.

All FAF data will be listed for the ITT set.

## 7. SAFETY ANALYSES

Safety analyses will be performed using the Safety set. Safety variables include adverse events (AEs), deaths, clinical laboratory results, vital signs, incidence of ADA against pegcetacoplan, ocular assessments (e.g., NL-BCVA, IOP and ophthalmic examinations), and ocular imaging.

At the time of the Month 12 reporting, safety summaries will be produced based on the complete Month 12 data. At the time of the final study reporting, safety summaries will be produced based on cumulative data.

For each safety variable, the last value collected before the first dose of investigational product will be used as baseline for all analyses of that safety variable. Last Observed Value (LOV) will be defined as the last valid assessment obtained after baseline. The LOV will be presented for the Month 12 reporting as well as the final study reporting.

All safety analyses will be conducted according to the actual treatment the subject received. Unless otherwise specified, all safety summaries will be performed on the Safety set.

### 7.1. Adverse Events

AEs will be coded using the MedDRA version 23.1 and summarized separately for those occurred in the study eye, those in the fellow eye, and the non-ocular events.

An AE will be considered a TEAE if it has a start date on or after the first dose of investigational product or if it has a start date before the date of the first dose of investigational product but increases in severity on or after the date of the first dose of investigational product.

An overall summary of the number of subjects with TEAEs will be presented, including the number and percentage of subjects with:

- Any TEAEs
- TEAEs related to study drug (evaluated by the investigator as definitely related, possibly related)
- TEAEs related to study drug injection procedure
- All TEAEs by maximum severity
- Serious TEAEs
- Serious TEAEs related to study drug (evaluated by the investigator as definitely related, possibly related)
- Serious TEAEs related to study drug injection procedure
- Serious TEAEs by maximum severity
- TEAEs leading to interruption of study treatment
- TEAEs leading to discontinuation of study treatment
- TEAEs leading to study discontinuation
- TEAEs leading to death

This overall summary will also include the total number of TEAEs reported. This overall summary will also be summarized separately for those occurred in the study eye, those in the fellow eye, and the non-ocular events.

The number and percentage of subjects reporting TEAEs in each treatment group and overall will be tabulated by SOC and PT for all of the categories in the list above. If more than 1 AE occurs with the same preferred term for the same subject, then the subject will be counted only once for that preferred term using the most severe and most related occurrence for the summarization by severity and by relationship to investigational product.

Endophthalmitis and intraocular inflammation ocular TEAEs will be presented by PT for study eye and fellow eye.

Endophthalmitis and intraocular inflammation ocular TEAEs in the study eye will also be presented on a per-injection basis (i.e., number of events/total number of injections given).

All SOC and PT summaries will be ordered alphabetically by SOC and within SOC, by descending order of the total number of subjects in the PM, PEOM, and Sham groups combined.

Non-ocular AEs, ocular AEs in the study eye and ocular AEs in the fellow eye will be listed separately. This presentation will be repeated for serious AEs. Additionally, separate listings for deaths, AEs leading to discontinuation of study, AEs leading to discontinuation of study drug, and AEs due to COVID-19 will also be generated.

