11.3.1. Relationship of Events to Study Treatment

All AEs that occur during this study will be recorded. The investigator will review each event and assess its relationship to study treatment (definitely related, possibly related, unlikely related, not related, unknown). The date and time of onset, time relationship to drug dosing, duration, and outcome (recovered/resolved, recovered/resolved with sequelae, recovering/resolving, not recovered/not resolved, fatal, or unknown) of each event will be noted.

The following definitions should be considered when evaluating the relationship of AEs and SAEs to the study treatment:

Definitely Related	Event or laboratory test abnormality, with plausible time relationship to drug intake						
Kelateu	Cannot be explained by disease or other drugs						
	Response to withdrawal plausible (pharmacologically, pathologically)						
	Event definitive pharmacologically or phenomenologically (ie, an objective and specific medical disorder or a recognized pharmacological phenomenon)						
	Re-challenge satisfactory, if necessary						
Possibly	Event or laboratory test abnormality, with reasonable time relationship to drug intake						
Related	Could also be explained by disease or other drugs						
	Information on drug withdrawal may be lacking or unclear						
Unlikely Related	Event or laboratory test abnormality, with a time to drug intake that makes a relationship improbable (but not impossible)						
	Disease or other drugs provide plausible explanations						
Not Related	Event or laboratory test abnormality, is plausibly related to the participant's clinical state, underlying disease, or the study procedure/conditions						
	Time relationship to drug intake makes a relationship unreasonable						
	Other obvious causes for event or laboratory test abnormality exist						
Unknown	Report suggests an adverse event, however, cannot be judged at this time because information is insufficient or contradictory						
	More data for proper assessment is needed, or additional data is under examination						

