### **13.7.5. Missing Relationship to Investigational Product for Adverse Events**

If the relationship to investigational product is missing for an AE starting on or after the date of the first dose of investigational product, a causality of "Related" to the investigational product will be assigned. The imputed values for relationship to double-blind investigational product will be used for incidence summaries, while both the actual and the imputed values will be presented in data listings.

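### Adverse events rated 'unknown' for causality are left out of the related counts, while events with a blank rating are counted as related

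*SAP*

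**What the plan says.** Protocol 11.3.1 asks the investigator to give each adverse event one of five ratings: "definitely related, possibly related, unlikely related, not related, unknown". The last applies when the event "cannot be judged at this time because information is insufficient or contradictory", or when further data are needed or still being examined. It is separate from the two levels that express doubt about, or rejection of, a causal link.

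SAP 7.1 plans two rows that use this scale, one for related TEAEs and one for related serious TEAEs, each limited to events "evaluated by the investigator as definitely related, possibly related". Both are repeated by system organ class and preferred term. A subject with several events of one preferred term is counted once, using the most severe and most related occurrence. SAP 7.1.1 repeats the overall summary for exudative AMD events in the study eye.

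SAP 13.7.5 covers absent ratings. Its trigger is "If the relationship to investigational product is missing for an AE starting on or after the date of the first dose of investigational product"; such events are assigned a causality of related, and the assigned value is used in the incidence summaries. Neither section says what happens to *unknown*.

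**The concern.** A blank rating and a rating of *unknown* both leave causality undetermined, yet one adds to the related rows and the other does not. Two events with the same facts could be tabulated differently because one site ticked *unknown* and another left the field empty.

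The treatment of *unknown* also departs from the SAP's pattern for incomplete adverse event data, which is to assume the less favourable case. Under SAP 13.7.3 an event with missing or partial dates is taken as treatment-emergent unless something contradicts that. Under 13.7.4 a missing severity on or after first dose becomes severe. Under 13.7.5 a missing causality becomes related. No reason is given for handling *unknown* differently.

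At stake are the related and serious-related rows, overall and by term, and the same rows in the exudative AMD summary. The question is most likely to arise at the Month 12 reporting, when the study is still running and some ratings may be awaiting data.

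**Working it through.** The documents give no figure to reproduce, because the point concerns a classification rule. Setting the three sections side by side:

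| Causality entry (protocol 11.3.1) | On the SAP 7.1 list? | Reached by SAP 13.7.5? | Counted as related? |
|---|---|---|---|
| Definitely related | Yes | No | Yes |
| Possibly related | Yes | No | Yes |
| Unlikely related | No | No | No |
| Not related | No | No | No |
| Unknown | No | No, a value is recorded | No |
| Blank, onset on or after first dose | No | Yes, set to related | Yes |

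1. The list in SAP 7.1 is closed: two ratings qualify and no residual wording brings in others.
2. SAP 13.7.5 acts only on a missing value. *Unknown* is a recorded value, so as written the rule does not reach it.
3. No other section fills the gap. Protocol 12.8 in one place describes related events as those the investigator considers definitively drug related. That also leaves out *unknown*, and SAP section 1 says that the SAP supersedes the protocol's analysis plan.
4. The rule that picks the most related occurrence needs an ordering of the ratings, and the SAP gives no place to *unknown*. A programmer would have to choose one.

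**Direction.** Let *k* be the number of subjects in an arm who have at least one event rated *unknown* and no event already counted as related. Treating *unknown* like a blank raises that arm's related row by *k*, and *k* cannot be negative. In a row for a single preferred term, *k* is counted within that term, so a subject already in the overall related row may still be added there.

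**Size.** The documents do not say how often *unknown* will be used. For scale only, take the planned 200 subjects per analysis group (the two sham arms of about 100 each are pooled) and assumed values of *k*. The change in percentage points is 100 × *k* / 200:

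- *k* = 0: 100 × 0 / 200 = 0
- *k* = 2: 100 × 2 / 200 = 1.0
- *k* = 5: 100 × 5 / 200 = 2.5
- *k* = 10: 100 × 10 / 200 = 5.0

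These values of *k* are illustrations, not estimates. A share of events could not be used in their place, because the tables count subjects and many subjects with an *unknown* event may already be in the related row.

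**The case against.** The strongest reply is that *unknown* and blank are different things. *Unknown* is a judgement the investigator made after review; a blank is an absent datum. Filling a gap conservatively while leaving a recorded rating alone is a defensible convention. The rating is also provisional: protocol 11.5 requires events to be followed up, and SAP 3.5 requires data to be reviewed and cleaned before each analysis, so an early *unknown* may be updated. The row label states exactly which ratings it reports, and the SAP list is wider than the definitively related wording in protocol 12.8.

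Much of this stands. It is why the proposed change applies only to ratings still *unknown* at the data cut, and why it keeps the investigator's own ratings visible. It does not remove the inconsistency: nothing in the documents requires an *unknown* to be resolved, and one that remains says no more about causality than a blank does.

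The reply on consequence also stands. The adverse event safety endpoint in SAP 2.2.5 is incidence and severity, not relatedness. All TEAEs, serious TEAEs, discontinuations and deaths are tabulated whatever the causality. So are endophthalmitis and intraocular inflammation (with per-injection rates for the study eye) and the incidence and time to onset of exudative AMD. An event rated *unknown* stays in those tables and in the listings.

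**Conclusion.** The inconsistency is real and minor. Under the SAP as written, *unknown* is not counted as related and blank is. The related rows can therefore be lower than the SAP's own rule for blanks would make them, by an amount that cannot be derived from the documents and may be zero. The conclusion rests on reading the SAP 7.1 list as complete and the 13.7.5 trigger literally.

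A reader might go further and infer that the SAP classes *unknown* events as unrelated, or that drug-related harm is understated. The documents do not support either. SAP 7.1 has no row for unrelated events and nowhere equates *unknown* with unrelated; the effect comes only from the list of ratings that qualify. Nothing shows that events rated *unknown* are in truth caused by the drug, so the shortfall is relative to the rule for blanks and not to a known true count.

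**What to change.** In SAP 7.1 and 13.7.5, state that a rating still *unknown* at the data cut is handled like a missing one: counted as related in the incidence summaries, with the recorded rating shown in the listings. Beneath each related row, add a row for subjects who are counted as related only through an *unknown* or an imputed rating. This row is a subset of the related row, not an additional count, so subtracting it recovers the number based on definite or possible ratings alone. In the most related occurrence rule, place *unknown* with the ratings that count as related, above unlikely related and not related.

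The cost is a sentence or two in each section and one extra row in the affected tables. No new data are needed and no efficacy analysis changes. The downside is that related counts may rise slightly; the subset row shows by how much.

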#### **7.1.1. TEAEs of New Onset Exudative AMD**

For subjects who experience a TEAE of “Choroidal neovascularization” or “Neovascular AMD” (“Exudative AMD TEAE”), the following summaries will be performed:

- The overall summary table described in Section 7.1 will be repeated replacing “TEAEs” with “Exudative AMD TEAEs”. This will be reported for the study eye.
- The incidence of Exudative AMD TEAEs in the study eye will be presented by treatment group and overall. In addition, the analysis will be repeated by fellow eye CNV status at baseline and study eye DLS on SD-OCT at baseline. A similar analysis will be repeated for the Exudative AMD TEAEs in the fellow eye with an additional analysis by fellow eye DLS on SD-OCT at baseline. Subjects with a medical history of CNV in the corresponding eye will be excluded from the analysis.
- The incidence and rate per 100 subject-years of Exudative AMD TEAEs in the study and fellow eye as well as a summary (for study and fellow eye) and Kaplan Meier plot for the time to development of Exudative AMD TEAEs in the study eye will be presented by treatment group and overall. Subjects with a medical history of CNV in the corresponding eye will be excluded from the analysis.
- In addition, the characteristics of the Exudative AMD TEAEs in the study eye will be presented at baseline, study visit preceding exudation, study visit at exudation and at Month 12 (or Month 24 if the final analysis) for characteristics based on SD-OCT and baseline, study visit at exudation and at Month 12 (or Month 24 if the final analysis) for characteristics based on Fluorescein Angiography (FA). The following characteristics will be presented by treatment group and overall:

- Presence of cystoid spaces on SD-OCT
  - Central (center point) retinal thickness on SD-OCT
  - Central subfield thickness on SD-OCT
  - Presence of CNV on FA.
  - CNV type on FA
  - Presence of subretinal fluid on SD-OCT
- A summary of concomitant anti-VEGF therapy for new exudative AMD in the study eye will be provided by treatment group and overall. This summary will include the total number of subjects that received any anti-VEGF for new exudative AMD as well as the average number of injections per month post exudative AMD. There will also be a breakdown by preferred term of ranibizumab or aflibercept and the average number of injections per month for each term. Subjects will be presented by the number of injections received for that medication.
  - BCVA scores at the baseline visit, study visit preceding exudation, the study visit at the exudation, and at Month 12 (or Month 24 if the final analysis) will be presented for all subjects with an Exudative AMD TEAE in the study eye by treatment group and overall. In addition, the change in BCVA scores from baseline, the visit prior to the exudation, and the exudation visit will be presented where appropriate.

A listing of Exudative AMD TEAEs and baseline characteristics including fellow eye CNV status, study eye double layer sign and study eye MNV presence, a listing of the characteristics of the new Exudative AMD TEAEs, anti-VEGF exposure, and the BCVA values for subjects with the new Exudative AMD TEAEs will be provided.

## 7.2. Clinical Laboratory Data

All laboratory parameters collected at each center's local laboratory will be normalized by converting values in original units to values in SI units and classified as normal, low, or high based on normal ranges supplied by the local laboratories and upon employing standardization.

Observed and change from baseline clinical laboratory data (hematology, chemistry and urinalysis) will be summarized by treatment group and protocol specified time points for the following clinical laboratory variables.

Hematology	Hemoglobin, hematocrit, red blood cells (RBC), platelet count, white blood cell count (WBC) – total and differential.
Biochemistry	Aspartate transaminase, alanine transaminase, alkaline phosphatase, sodium, potassium, chloride, bicarbonate, blood urea nitrogen (BUN), bilirubin (total, direct and indirect), creatinine, creatine kinase, glucose, and albumin.
Urinalysis	Glucose, specific gravity, blood, ketones, protein, bilirubin, pH, urobilinogen, leukocyte esterase, and nitrite.

Clinical laboratory test values are potentially clinically significant (PCS) if they meet either the low or high PCS criteria listed in [Table 3](#). The number and percentage of subjects with baseline and/or post-baseline PCS values will be tabulated by treatment group and overall.

The percentages will be calculated relative to the number of subjects with available values for

each lab parameter in each treatment group at the analysis visit. The numerator is the total number of subjects with at least 1 PCS value at the analysis visit. A supportive listing of subjects with post-baseline PCS values will be provided including the subject number, site, baseline, and post-baseline values.

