#### **2.2.5. Safety Endpoints**

- Incidence and severity of ocular and systemic treatment-emergent adverse events.
- Incidence of ADA directed against pegcetacoplan peptide or PEG.
- Incidence of new active CNV in the study eye.
- Incidence of new onset of subclinical CNV in the study eye.
- Incidence of subjects who lost letters based on NL-BCVA categories ( $\geq 15$ ,  $\geq 15 < 30$ ,  $\geq 30$  ETDRS letters).
- Change/shift from baseline in clinical labs and incidence of abnormal lab values.
- Change from baseline in vital signs and incidence of abnormal vital sign results.
- Shift from baseline in ocular examination assessments including slit-lamp examination and indirect ophthalmoscopy.
- Change from baseline in Intra Ocular Pressure (IOP) and incidence of IOP above specified thresholds.
- Change/shift from baseline in ocular imaging assessments (including specular microscopy; select sites).

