**Table 3: Criteria for Potentially Clinically Significant Laboratory Tests**

Parameter	SI Unit	Lower Limit	Higher Limit
Biochemistry			
Albumin	g/L	<25 g/L	
Alanine Aminotransferase (ALT)	U/L		≥3*ULN
Alkaline Phosphatase (ALP)	U/L		≥3*ULN
Aspartate Aminotransferase (AST)	U/L		≥3*ULN
Bilirubin, Direct	umol/L		>1.5*ULN
Bilirubin, Total	umol/L		>1.5*ULN
Bicarbonate	mmol/L	<LLN	
Blood Urea nitrogen	mmol/L		>2.5*ULN
Chloride	mmol/L	<90 mmol/L	>115mmol/L
Creatinine	umol/L		≥178.8 umol/L
Creatine kinases	U/L		≥3*ULN
Glucose	mmol/L	<3.05 mmol/L	≥8.88 mmol/L
Potassium	mmol/L	<3.5 mmol/L	>5.5 mmol/L
Sodium	mmol/L	<130 mmol/L	>150 mmol/L
Hematology			
Hemoglobin	g/L	<0.9*LLN	
Hematocrit	%	<0.9*LLN	
Platelet Count	10  /L	<LLN	
Urinalysis			
Specific Gravity		<0.9*LLN	>1.1*ULN
pH		<LLN	
Protein			>2+
Glucose			>1+
Blood			>2+

LLN: Lower limit of normal value provided by the laboratory  
 ULN: Upper limit of normal value provided by the laboratory

Descriptive statistics will be used for continuous data and frequency counts and percentages for categorical data. A shift table from baseline, by treatment group and protocol specified time points, of normal, abnormal low, and abnormal high records will also be summarized for hematology and chemistry data with marginal totals using frequency counts and percentages.

All laboratory data will be listed for the safety set.

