**Table 4: Criteria for Potentially Clinically Significant Vital Signs**

Vital Sign Parameter	Flag	Criteria a	
		Observed Value	Change from Baseline
Systolic blood pressure (mmHg)	High	≥180	Increase of ≥20
	Low	≤90	Decrease of ≥20
Diastolic blood pressure (mmHg)	High	≥105	Increase of ≥15
	Low	≤50	Decrease of ≥15
Pulse rate (beats per minute)	High	≥120	Increase of ≥15
	Low	≤50	Decrease of ≥15

a A post-baseline value is considered as a PCS value if its meets both criteria for observed value and change from baseline.

All vital signs data will be listed for the safety set.

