### **13.6. Repeated or Unscheduled Assessments of Safety Parameters**

If a subject has repeated assessments before the start of investigational product, then the results from the final assessment made prior to the start of investigational product will be used as baseline. If end-of-study assessments are repeated or unscheduled, the last post-baseline assessment will be used as the end of study assessment for generating descriptive statistics. However, all post-baseline assessments will be used for PCS value determination and all assessments will be presented in the data listings.

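### SAP 7.2 reports potentially clinically significant (PCS) laboratory values as prevalence at each visit and defines no by-arm count of new ones

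*SAP*

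**What the plan says.** SAP 2.2.5 includes among the safety endpoints: "Change/shift from baseline in clinical labs and incidence of abnormal lab values".

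SAP 7.2 applies the limits in Table 3 and states: "The number and percentage of subjects with baseline and/or post-baseline PCS values will be tabulated by treatment group and overall". The percentage is relative to subjects with a value available for "each lab parameter in each treatment group at the analysis visit". On the numerator it says: "The numerator is the total number of subjects with at least 1 PCS value at the analysis visit". Nothing removes a subject who was PCS at baseline, requires worsening, or defines a count over the whole post-baseline period.

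Three other provisions bear on the point:

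- SAP 7.2 adds a listing: "A supportive listing of subjects with post-baseline PCS values will be provided including the subject number, site, baseline, and post-baseline values".
- SAP 7.2, below Table 3, plans for hematology and chemistry: "A shift table from baseline, by treatment group and protocol specified time points, of normal, abnormal low, and abnormal high records".
- SAP 13.6 says that "all post-baseline assessments will be used for PCS value determination".

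For vital signs, the footnote to Table 4 reads: "A post-baseline value is considered as a PCS value if its meets both criteria for observed value and change from baseline". Table 3 has no such condition.

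**The concern.** Incidence concerns events that arise in people who did not have them at the start. A visit-by-visit percentage with everyone measured in the denominator is prevalence. A subject with a stable chronic abnormality counts at baseline and again at every later laboratory visit.

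This is plausible here. Subjects are at least 60 years old. Exclusion criterion 16 rests on the investigator's view of the screening values and not on the Table 3 limits, so a subject with, say, glucose of at least 8.88 mmol/L or platelets below the lower limit of normal can enter.

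At stake is how clearly the report can say, by arm, how many subjects developed a new PCS value. A background shared by all arms makes a true increase look smaller in relative terms, and transient abnormalities at different visits are never added up per subject.

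**Working it through.** The documents state no laboratory rate, so there is no figure to reproduce. The check sets the provisions side by side and then illustrates the dilution.

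**1. What each planned output can show about new PCS values**

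- *PCS table (7.2).* By visit; baseline PCS subjects stay in numerator and denominator. It gives prevalence.
- *Shift table (7.2).* By time point, in normal/low/high categories. For platelets and bicarbonate the PCS limit is the lower limit of normal, so a shift from normal to low is a new PCS value. For most other parameters the limits differ. ALT is PCS at 3 times the upper limit or more, so a subject going from 1.2 to 5 times the upper limit stays high-to-high although the value is newly PCS. The table omits urinalysis, for which Table 3 sets limits on five parameters (specific gravity, pH, protein, glucose, blood), and it is not cumulative.
- *Listing (7.2).* Shows baseline beside post-baseline values per subject, but gives no count or rate by arm.
- *Adverse events (Protocol 9.6, SAP 7.1).* Clinically significant laboratory values are recorded as adverse events and count as treatment-emergent if they start or worsen on or after first dose. This is a cumulative by-arm count, but it depends on the investigator's judgement and not on Table 3.

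None of the four gives new PCS values by arm for all Table 3 parameters.

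**2. How far pre-existing values can dilute the contrast**

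Inputs from the documents: about 200 subjects per group (SAP 3.4, shams pooled) and five scheduled post-baseline safety-laboratory visits, at Months 2, 6, 12, 18 and 24 (SAP Tables 9 to 12).

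Assumed inputs: a proportion b is PCS at baseline and remains so; among the rest, a proportion h has a transient PCS value at each visit, independently across visits, with h = 3% on sham and 6% on active.

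Visit table = b + (1 − b) × h.

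New PCS at any of five visits among subjects not PCS at baseline = 1 − (1 − h)^5.

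- b = 2%: 0.02 + 0.98 × 0.03 = 4.9%; 0.02 + 0.98 × 0.06 = 7.9%; ratio 1.60.
- b = 10%: 0.10 + 0.90 × 0.03 = 12.7%; 0.10 + 0.90 × 0.06 = 15.4%; ratio 1.21.
- b = 20%: 0.20 + 0.80 × 0.03 = 22.4%; 0.20 + 0.80 × 0.06 = 24.8%; ratio 1.11.
- New PCS at any visit, whatever b: 1 − 0.97^5 = 14.1%; 1 − 0.94^5 = 26.6%; ratio 1.88. With b = 10% this is based on 200 × 0.90 = 180 subjects per group.

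With h = 1% and 3% instead, the visit-table ratio runs from 1.66 (b = 2%) to 1.08 (b = 20%), against 2.88 for new PCS values.

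The per-visit risk difference moves much less: with b = 10% it is 15.4 − 12.7 = 2.7 points, against 6 − 3 = 3 points among subjects not PCS at baseline. The loss is mainly in the relative contrast and in the missing cumulative count.

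**The case against.** A reader might infer that the plan hides new laboratory abnormalities. The documents do not support that. The listing puts baseline and post-baseline values side by side, the shift table separates subjects normal at baseline, clinically significant values become adverse events, and the PCS tabulation includes baseline, so the pre-existing burden is visible by arm.

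Further points on that side:

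- *The endpoint says abnormal, not PCS.* This is fair: the shift table answers part of it. It still does so by time point, without urinalysis, and mostly at other limits.
- *The word incidence is used loosely in this SAP.* SAP 7.5 applies it to intraocular pressure above thresholds without a baseline exclusion. That softens the charge of inconsistency but does not supply the missing count.
- *The vital-signs rule is not a precedent.* Correct. Table 4 requires worsening, not a non-PCS baseline, and 7.3 uses the same by-visit numerator. It shows only that baseline was considered there and not in Table 3.
- *A count over all post-baseline assessments may be intended.* SAP 13.6 leaves this open. But 7.2 defines numerator and denominator by visit, and 13.4.1 by default uses unscheduled results in summaries over time only when the scheduled result is missing. The three need reconciling.
- *The size is assumed, and relevance is low.* Many Table 3 limits lie far from normal, criterion 16 removes some subjects, and Protocol 4.1.3 describes serum levels after intravitreal dosing as far below those from systemic routes. SAP 7.2 plans no test, so an argument from lost statistical information has little force. All of this stands and keeps the point minor.

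**Conclusion.** The point holds as a small, inexpensive improvement. As written, SAP 7.2 gives visit-level prevalence of PCS values, including those present at baseline, and no by-arm count of new ones, while 2.2.5 names incidence. The other outputs cover this in part. What remains is the parameters whose PCS limit differs from the normal range, urinalysis, and the cumulative count.

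The direction of the dilution follows from the definition whenever some baseline PCS values persist. Its size cannot be stated: the ratios above rest on assumed baseline, persistence and onset rates, and are illustrations only. The primary analysis, the type I error control and the conduct of the trial are unaffected.

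**What to change.** In SAP 7.2 add one row or table of treatment-emergent PCS values, for each parameter and direction:

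- *Numerator:* subjects not PCS in that direction at baseline who have at least 1 PCS value at any post-baseline assessment, scheduled or unscheduled.
- *Denominator:* subjects not PCS in that direction at baseline with at least 1 post-baseline value.

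Keep the by-visit table as support. State that the new row follows 13.6, so that unscheduled values count even where 13.4.1 would leave them out of a by-visit summary.

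The cost is a change of SAP wording and one more descriptive output from data already collected. The small downside is that denominators will vary by parameter.
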